4.4.3. Main study, end-of-study visits

The subject and informant will be requested to visit the clinic for an end-of-study visit. Optionally, the Amsterdam IADL scale will be administered with the caregiver/informant, and the CERAD neuropsychological test battery will be repeated with the study subject.

Wearable devices will be recovered and the apps uninstalled from the smartphone. For those subjects that will leave the study, a brief assessment of their health condition will be performed with an interview and they will be dismissed. For those individuals and their caregiver/family member that confirm the interest in joining the sub-study, signature of the ICF for the sub-study will be requested. Arrangement of a date in the following 2-3 weeks for a technical visit at home for feasibility of the installation of the fixed devices. A hot-line for technical assistance will be made accessible via smartphone.

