Objectives: The primary objective of this study is to assess the performance of selected RMTs against standardised rating scales of ADLs in subjects with preclinical AD dementia, MCI due to AD dementia, and mild-to-moderate AD dementia. Secondary objectives are, (a) to evaluate associations between RMTs and standard clinical scales used to characterise people with AD diagnosis, (b) to investigate the patient acceptability of selected RMTs used for the duration of the study, and (c) to assess the technical performance of RMTs and digital platform in a real-life setting.

Study design: A multicentre observational cross-sectional cohort digital assessment study lasting 5 years, with a sub-study extension of at-home monitoring for 4 weeks.

Study population: Subjects (n=283) with positive AD biomarkers, e.g positive brain Abeta (A β) deposition confirmed by amyloid PET or CSF A β test at the preclinical AD, MCI due to AD, and mild-to-moderate AD dementia stages, and age-and gender matched control subjects (n=213) aged over 50 years with a caregiver/family member available to contribute to the study.

Primary outcome measure: statistically significant difference between healthy volunteers, preclinical AD, MCI due to AD, and mild-to-moderate AD dementia in outcome measures of ADL using selected RMTs.

1. **Secondary Outcome measurements:** Statistically significant difference between healthy volunteers, preclinical AD, MCI due to AD, and mild-to-moderate AD dementia using RMTs, neuropsychological assessment like CDR and Altoida's cognitive scale. Finally the relationship of genes or biomarkers with risk of RMT progression, and longitudinal correlation changes in biomarkers with rate of RMT progression.

Evaluation of a Computerized Complex Instrumental Activities of Daily Living Marker (NMI) (AltoidaML)

2. Assess effectiveness of disease modifying therapy such as aducanumab in real world clinical practice on subjects who will initiate disease modifying therapy for AD treatment during the study by using neuropsychological assessment such as CDR and fluid biomarker including blood and CSF and so on.
3. Assess effectiveness of disease modifying therapy such as aducanumab in real world clinical practice on subjects who will initiate disease modifying therapy for AD treatment during the study by using RMTs and Altoida's cognitive scale.

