| | | Smoking | Once | 5 | Life habits & AD risk factors |
|--|--|---------|------|---|-------------------------------|

Evaluation of a Computerized Complex Instrumental Activities of Daily Living Marker (NMI) (AltoidaML)

2. Study design

The study is a multicentre, observational, cross-sectional, digital assessment cohort study in subjects with preclinical AD, MCI due to AD, and mild-to-moderate AD dementia. It consists of two parts: the main study (tier 1), where the subjects are provided with wearable digital devices, and a sub-study (tier 2), in which technologies are installed in the subjects' home (see table 2 above). The duration of the main study for individual subjects is 5 years of data collection, while for the sub-study (tier 2) a similar period of data collection is expected, with a flexible time between the two studies for arranging home-device wiring. The sub-study will be performed on those volunteers whose home setting shows the necessary technical requirements (please see table 2 above for the Residential Movement Detector).

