4.4.5. Sub-study, study-end call or visit

At the end of the time agreed for the sub-study, a phone call will be made to the subject and/or the caregiver/informant to provide instructions about uninstalling the device and to send

Evaluation of a Computerized Complex Instrumental Activities of Daily Living Marker (NMI) (AltoidaML)

the device back by mail. Alternatively, one representative of the technical team will visit the house and recover the device. Timing is relevant since the same devices will be used again to wire the house of the next participant. A brief survey and few questions about the device use and acceptability will be asked, including AEs or the overall impact of this experience for the subjects and caregiver/informant.

8. RMT/digital technology use in real life

In this study, the presence of an active caregiver/informant is critical for keeping the proper adherence to the study protocol of the subjects and to provide specific information about when a certain ADL is performed by the subject. Caregivers will share some of the same smartphone apps uploaded for the subjects and will receive the same notification, so to help the subject to keep schedule, and may opt for the use of other devices.

2. Main study

The devices included in the study, smartphone applications (aps), were selected according to a series of criteria that minimize the burden to the subjects while delivering information about the time and context in which the ADL is performed. Occasionally, for a few days during the study, the subject will be asked to wear a portable camera that does not broadcast images. Subjects will be instructed: (a) to always keep the smartphone close to them and, when walking outside home, to keep it in a belt holder or trouser pocket and (b) to always wear a wrist-band accelerometer on the dominant hand during the day and for most of the nights.

The following devices will be used:

- The smartphone app Altoida NMI telehealth version, an active interface to collect subject inputs on
 - Orientation, planning skills & spatial memory required for task completion.
 - Executive function skills & prospective memory required for task completion, short and long term.
 - Mood & anxiety
 - Voice & speech analysis
 - Accelerometer, dominant hand - arm movement,
 - Gait and motility at home etc.

Evaluation of a Computerized Complex Instrumental Activities of Daily Living Marker (NMI) (AltoidaML)

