4.4.6. Sub-study

Fixed devices will be installed and connected with the WiFi router to monitor activity in the various part of the house, for assessing motility in the various part of the house at various time of the day during specific activities (communicated via smartphone EMA).

Evaluation of a Computerized Complex Instrumental Activities of Daily Living Marker (NMI) (AltoidaML)

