7. ETHICAL CONSIDERATIONS

17. Regulation statement

The study will be carried out in accordance with the ethical conduct and juridical laws of the *Declaration of Helsinki* 59th WMA General Assembly, Seoul, October 2008, (www.wma.net), and in accordance with the GDPR regulations and WMO.

18. Recruitment and consent

Supervising doctors and researchers at the research sites will screen participants for eligibility. If eligible the candidate will be informed orally and in writing (i.e. an information letter) about the study and asked to participate. The aim of the study and the procedure will be explained to the participant. Participants are informed that they can withdraw from the

Evaluation of a Computerized Complex Instrumental Activities of Daily Living Marker (NMI) (AltoidaML)

study at any point of the study without any consequences. It is made clear that withdrawal from the study will not affect further treatment or legal rights. The participant will have a sufficient amount of time (i.e. at least 7 days) before making a decision about involvement in the study. Subsequently, the participant is asked to sign an informed consent form according to the national guidelines. After the informed consent is signed, data will be collected during the baseline visit. All materials will be used according to national ethical guidelines for Good Clinical Practice.

19. Objection by minors or incapacitated subjects

The minimal MMSE score for participation is 17, which means that no incapacitated subjects are allowed to participate in the study.

20. Benefits and risks assessment, group relatedness

Benefits:

There is no direct benefit for the participant. This study may lead to the discovery of early diagnostic and prognostic markers and novel treatment targets for Alzheimer's disease, which will be a benefit for future patients with AD.

Risks:

Neurophysiological testing might be tiresome. The RMTs have to be used every day, which might lead to discomfort.

21. Compensation for injury

The sponsor/investigator has a liability insurance which is in accordance with article 7 of the WMO. The sponsor (also) has an insurance which is in accordance with the legal requirements in the Netherlands (Article 7 WMO). This insurance provides cover for damage to research subjects through injury or death caused by the study. The insurance applies to the damage that becomes apparent during the study or within 4 years after the end of the study.

22. Incentives

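### Apps and wearables are removed at the end-of-study visit with no exception for participants entering the at-home sub-study, which relies on smartphone activity reports; durations, consent timing and the stage used also need reconciling

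*Combined protocol and SAP*

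**What the plan says.** **Order and length.** The Study design part of section 2 says of tier 1: "The duration of the main study for individual subjects is 5 years of data collection". For tier 2 it continues "while for the sub-study (tier 2) a similar period of data collection is expected", and it places the two parts one after the other, "with a flexible time between the two studies for arranging home-device wiring". The Summary instead describes the study "with a sub-study extension of at-home monitoring for 4 weeks". Section 4.4.5, on the return of the home sensors, adds: "Timing is relevant since the same devices will be used again to wire the house of the next participant". Section 6 (Statistical analysis) aggregates continuous device data over an experiment of 8 weeks.

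**Devices.** Section 4.4.3, on the end-of-study visit: "Wearable devices will be recovered and the apps uninstalled from the smartphone". The same paragraph then separates those who leave from those who join tier 2. The joiners are asked to sign the sub-study consent, and a home visit is arranged 2 to 3 weeks later. Section 4.4.6 has the fixed sensors assess movement around the house "at various time of the day during specific activities (communicated via smartphone EMA".

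**Consent.** The inclusion criteria for both patients and controls list the additional sub-study consent, and section 4.4.1 provides its addendum around screening. Section 4.4.3 asks for the signature at study end. Section 7 (item 19) states: "The minimal MMSE score for participation is 17, which means that no incapacitated subjects are allowed to participate in the study".

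**Staging.** Stage at entry rests mainly on MMSE and CDR, obtained no more than 6 months before screening (section 4.4.1). Table 2 lists CDR as annual. Section 4.4.2 and the clinic assessments describe MMSE as longitudinal, although Table 2 lists it once.

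**The concern.** Fixed home sensors record that someone moved, where and when. To read this as performance of a daily activity, the analyst must know which activity was under way. Section 4.4.6 gets that from the smartphone. If the app goes at the visit where tier 2 begins and nothing restores it, the sensor record has no main source of activity labels.

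The other gaps concern how tier 2 data could be analysed. Without one stated duration per part, neither the amount of tier 2 data nor the time between staging and tier 2 is defined. If that time is 5 years in a disease the protocol assumes to worsen, group comparisons in tier 2 by entry stage would mix people who have progressed with people who have not. No rule says which stage is used. Sub-study consent has two possible times, and the protocol's reasoning about capacity may not serve both equally well.

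**Working it through.** The plan gives no figure to reproduce here. The check is a comparison of sections, with simple arithmetic to size the staging point.

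**1. Is there a route for activity tags in tier 2?**
- Section 4.4.3: wearables and apps are removed, with no exception for joiners.
- Section 4.4.4: fixed sensors are installed and the household is trained on them. No app or wrist device is mentioned.
- Section 4.4.5: covers the return of the home sensors and a short survey.
- Section 4.4.6: relies on smartphone reports of activity.

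No step between removal and use puts the app back. The secondary outcomes in section 2 name the subject, the caregiver and a portable camera (when available) as sources of time-tagged epochs. The caregiver's channel includes study apps installed at baseline (section 4.4.2), and 4.4.3 does not say that these are kept. The camera is optional and worn for a few days of the main study. Both are partial substitutes. This result does not depend on how long either part lasts.

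**2. How far apart are the stated durations?**
- Tier 2: 5 × 365.25 / 28 = 65.2, so one reading is about 65 times the other.
- Main study: 5 years (Summary and section 2) against 8 weeks (section 6). Section 3 also asks for at least 2 years of data before a participant's data are used, which does not fit 8 weeks.
- Time from baseline to the end of tier 2, with 3 weeks between the parts and 52.18 weeks to the year:
  - 5 years + 3 weeks + 4 weeks = 5 + 7/52.18 = about 5.1 years
  - 5 years + 3 weeks + 5 years = 10 + 3/52.18 = about 10.1 years
  - 8 + 3 + 4 = 15 weeks

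**3. How many could have left their entry stage when tier 2 begins?** The documents give no progression rate. For an assumed constant yearly rate r, the share who have moved after t years is 1 − (1 − r)^t.

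| Assumed r | t = 5 years | t = 8 weeks (8/52.18 years) |
|---|---|---|
| 1% | 4.9% | 0.15% |
| 2% | 9.6% | 0.31% |
| 5% | 22.6% | 0.78% |
| 10% | 41.0% | 1.6% |
| 15% | 55.6% | 2.5% |
| 20% | 67.2% | 3.4% |

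The staging point is material under the 5-year duration and nearly disappears under 8 weeks.

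**4. When is sub-study consent given?** The inclusion criteria and section 4.4.1 point to entry, and section 4.4.3 to study end. The MMSE statement in section 7 is tied to participation. No section says whether it is checked again at a later sub-study signature.

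**The case against.** The strongest reply is that tier 2 is openly unfinished. Section 4.4.4 bars its start until an amendment specifies the fixed sensor, section 4.4.6 itself presumes a smartphone function, and participants use their own phones, so an app can be reinstalled. This stands in part: reinstallation is not ruled out. But the amendment is required only to specify the device, so the gap could survive it.

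Four stronger readings are tempting, and the documents do not support them.
- **Activity tags are lost altogether.** A reader might infer this from 4.4.3, but other sources are named, and section 4.4.4 also gives the sensors uses, such as sleep and activity patterns, that are not stated to need tags.
- **Tier 2 participants are no longer at their entry stage.** No progression rate is given, and annual CDR with longitudinal MMSE would allow re-staging. What is missing is a rule on which stage to use.
- **Consent is taken from people without capacity at year 5.** That uses only one side of the consent timing. The MMSE minimum can be read as covering participation in either part, and it is unclear whether the word making the Amsterdam IADL optional at the last visit also governs the test battery that contains MMSE.
- **Tier 2 must run alongside the wearables near baseline.** The Summary calls tier 2 an extension and section 2 plans a gap, so the sequence is deliberate. No stated objective requires fixed sensors and wearables to run together, and the home sensors rotate between houses.

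**Conclusion.** The point holds as a conflict between sections 4.4.3 and 4.4.6. Followed as written, tier 2 starts without the main route the protocol names for labelling activities, and the named alternatives replace it only in part. This needs no assumption.

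Three further inconsistencies are textual and also hold: the length of tier 2 (about 65-fold between readings), the length of the main study (5 years against 8 weeks), and the time of sub-study consent.

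The staging point is conditional. If the main study lasts 5 years, the entry stage may be out of date for an unknown share of tier 2 participants. The range of about 5% to 67% rests wholly on assumed constant yearly rates of 1% to 20%. At 8 weeks it would be about 0.2% to 3.4%.

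The missing tags and the choice of stage weaken what tier 2 can show. They do not bear on the tier 1 group comparisons.

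**What to change.** Make these changes in the amendment that section 4.4.4 already requires before tier 2 can start:

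1. In 4.4.3, limit app removal and wearable recovery to participants not entering tier 2. State in 4.4.4 to 4.4.6 that the app and wrist device stay in use until tier 2 ends, and say whether the caregiver's app stays too.
2. Reconcile the Summary, the Study design part of section 2 and section 6, so that each part has one stated duration.
3. Reconcile the time of sub-study consent across the inclusion criteria, 4.4.1 and 4.4.3, and state how the MMSE statement in section 7 applies at that time.
4. In section 6, state that tier 2 analyses use the stage from the most recent annual CDR and longitudinal MMSE rather than the entry stage. Align the MMSE frequency in Table 2 with the text that calls it longitudinal.

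The cost is protocol wording, plus apps and wrist devices staying with tier 2 participants for longer. No new assessment is needed if MMSE is collected longitudinally as the text says. Running tier 2 alongside the main study near baseline is an option for the sponsor, not a required correction. It could not reach participants already past that window when the amendment is approved, and it might need more home sensors.

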4.4.4. Sub-study, baseline home visits for device installation

During the in-home visit, feasibility for the wiring and installation of the device will be conducted as essential entry criterion by the technical team. Fixed devices will be installed and connected with the WiFi router to monitor activity in various parts of the home, for profiling some social aspects of interpersonal interactions and for more precise sleep-activity patterning. The technical team will take notes on the size and structural features of the house, the household members and other relevant questions, as described in the ICF. Some training about the device characteristics, instructions about the use and location in the house will be performed for the household members. The sub-study will only start when an amendment is approved which specifies the type of device used as fixed sensor in-home.

4.4.5. Sub-study, study-end call or visit

At the end of the time agreed for the sub-study, a phone call will be made to the subject and/or the caregiver/informant to provide instructions about uninstalling the device and to send

Evaluation of a Computerized Complex Instrumental Activities of Daily Living Marker (NMI) (AltoidaML)

the device back by mail. Alternatively, one representative of the technical team will visit the house and recover the device. Timing is relevant since the same devices will be used again to wire the house of the next participant. A brief survey and few questions about the device use and acceptability will be asked, including AEs or the overall impact of this experience for the subjects and caregiver/informant.

8. RMT/digital technology use in real life

In this study, the presence of an active caregiver/informant is critical for keeping the proper adherence to the study protocol of the subjects and to provide specific information about when a certain ADL is performed by the subject. Caregivers will share some of the same smartphone apps uploaded for the subjects and will receive the same notification, so to help the subject to keep schedule, and may opt for the use of other devices.

2. Main study

The devices included in the study, smartphone applications (aps), were selected according to a series of criteria that minimize the burden to the subjects while delivering information about the time and context in which the ADL is performed. Occasionally, for a few days during the study, the subject will be asked to wear a portable camera that does not broadcast images. Subjects will be instructed: (a) to always keep the smartphone close to them and, when walking outside home, to keep it in a belt holder or trouser pocket and (b) to always wear a wrist-band accelerometer on the dominant hand during the day and for most of the nights.

The following devices will be used:

- The smartphone app Altoida NMI telehealth version, an active interface to collect subject inputs on
 - Orientation, planning skills & spatial memory required for task completion.
 - Executive function skills & prospective memory required for task completion, short and long term.
 - Mood & anxiety
 - Voice & speech analysis
 - Accelerometer, dominant hand - arm movement,
 - Gait and motility at home etc.

Evaluation of a Computerized Complex Instrumental Activities of Daily Living Marker (NMI) (AltoidaML)

4.4.6. Sub-study

Fixed devices will be installed and connected with the WiFi router to monitor activity in the various part of the house, for assessing motility in the various part of the house at various time of the day during specific activities (communicated via smartphone EMA).

Evaluation of a Computerized Complex Instrumental Activities of Daily Living Marker (NMI) (AltoidaML)

1. ASSESSMENTS

9. Assessments in the clinic

Demographics

- Date of original informed consent
- Date of birth
- Resident location, e.g. zip code.
- Gender
- Ethnicity
- Referral source
- Education (highest level attained), registered as number of years of formal education.
- Occupation
- Marital status
- Living situation (e.g., lives alone, lives with spouse/partner).
- Handedness, established using the Edinburgh Handedness Inventory Form [6].

Medical history and medication use

- Diabetes or pre-diabetes
- Episodes of depression in adult life.
- Other relevant medical history
- Current medication use, pharmaceutical name and dose

Physical examination

- Body height
- Body weight
- Body Mass Index (BMI) and height will be measured at the baseline visit only.
- Blood pressure measured after the subject has been lying down for 3-5 minutes; following the supine blood pressure, the subject will stand and blood pressure and heart rate will be taken again after 2-3 minutes.

Life habits & AD risk factors

- Diet supplement use, as indicated by the NIH website a series of supplements are commonly used in ageing, even supporting evidence for their benefits in AD are not conclusive (<https://nccih.nih.gov/health/providers/digest/alzheimers>). They are: vitamins B, vitamin E, folate, coconut oil, ginkgo, omega-3 fatty acids/fish oil, vitamins B and E, Asian ginseng, grape seed extract, and curcumin [7].

Evaluation of a Computerized Complex Instrumental Activities of Daily Living Marker (NMI) (AltoidaML)

- Godin Leisure-time exercise questionnaire for assessment how many times a series of different kinds of exercise are performed on average for more than 15 minutes during a typical week [8].
- Smoking habits, including life-time smoking ("when the smoking habit started") and amount ("how many pack of cigarettes per months were smoked in the last year").
- Drinking habits. Assessment of alcohol use, expressed in units consumption per day.
- Hobbies, listed as reported number of activities-hobbies / week (i.e., reading, crossword, puzzle solving, listening or playing music, painting, gardening, backing) for how long time (hour/week) [9].

Evaluation of a Computerized Complex Instrumental Activities of Daily Living Marker (NMI) (AltoidaML)

Questionnaires (filled out by study subject)

- *CERAD neuropsychological test battery*: is a well-established assessment [10] that explores the following cognitive dimensions:
 - *Verbal fluency (animal naming)* [11]
 - *15 item Boston Naming Test* [12]
 - *Word list learning* [13]
 - *Word list recall* [13]
 - *Word list recognition* [13]
 - *Constructional praxis*: Rey Complex Figure drawing [14]
 - *Delayed constructional praxis*: Rey Complex Figure recall [14]
- *Mini-Mental State Examination (MMSE)*. The MMSE is a 30-item mental status questionnaire that assesses a participant's mental status (orientation, memory, attention, language, visual-spatial abilities, and calculation). A total MMSE score is calculated by summing all correct items out of a possible 30 points. The utility of MMSE, along with global indicators such as CDR, is principally as a clinical descriptor. MMSE was included in the standard clinical assessment as a standard measure that is regularly used in studies and recognized by regulatory authorities [15]. In this study, the MMSE is used longitudinally.
- *Digit Symbol Substitution Test (DSST)* [16] is a neuropsychological performance test that explores attention, working memory and executive functions.
- *Pittsburgh Sleep Quality Index (PSQI)*. The Pittsburgh Sleep Quality Index is a self-rated questionnaire that assesses sleep quality and disturbances over a one-month time interval. Nineteen items generate seven component scores: subjective sleep quality, sleep latency, sleep duration, habitual sleep efficiency, sleep disturbances, use of sleep medication, and sleep-related daytime dysfunction. The sum of scores for the seven components gives a global score. The index has adequate internal consistency and high retest reliability, with a diagnostic discriminability of 89.6% sensitivity and 86.5% specificity for good and poor sleepers [17].
- *Epworth Sleepiness Scale (ESS)*. The Epworth Sleepiness Scale is a self-reported questionnaire and it is used to determine the level of daytime sleepiness [18]. A score of 10 or more is considered sleepy. A score of 18 or more is very sleepy.
- *Social Functioning Scale (SFS)*. A questionnaire to assess social functioning, initially developed for schizophrenic patients [19].

Evaluation of a Computerized Complex Instrumental Activities of Daily Living Marker (NMI) (AltoidaML)

- *Geriatric Depression Scale (GDS)* The GDS is a 30-item self-report assessment recorded by the clinician, used to identify depressive symptomatology in the elderly. The GDS questions are answered "yes" or "no". One point is assigned to each answer and the cumulative score is rated on a scoring grid. The grid sets a range of 0-9 as "normal", 10-19 as "mildly depressed", and 20-30 as "severely depressed". A diagnosis of clinical depression should not be based on GDS results alone. The test has well established reliability and validity with 92% sensitivity and 89% specificity when evaluated against diagnostic criteria. Although a shorter version (15 items) has been validated, the longer version is more likely to have a normal distribution—hence better adapted for use as a dimensional scale—without reliance on theoretical clinical cut-off points. The larger range of items also permits a finer analysis by symptom cluster and not just overall score [20].
- *Test of proficiency in the use of smartphone communication apps.* After all apps will be installed on the smartphone and training for the devices performed, the subjects will be asked to fill a brief questionnaire about which communication apps they are familiar with, e.g., phone calls, SMS messaging, WhatsApp, Facebook, Skype, Instagram, etc. The rater will ask the subject to perform some tasks using the smartphone, such as: (a) place a phone call to home; (b) place a phone call to a new number, (c) send an SMS – an agreed short text; (d) start a WhatsApp (or alike app) chat with at least 3 exchanges of conversation with their caregiver that sit in another room; (e) send a picture; (f) read the last arrived email. The rater will score dexterity, self-assurance and efficiency on a VAS (1-5 points).

The subject and the caregivers will be asked to answer to 4 questions about Smartphone Technology use (score 1-10 with 1 minimum and 10 maximum of agreement): (1) “Using the smartphone, tablet or PC technology enhance my effectiveness for daily activities”, (2) I find these technologies quite easy to use”, (3) “ I feel apprehensive when using these technologies, with sometime fear of making mistakes”; (4) “I have difficulties in concentrating and maintain attention when using these technologies”.

Questionnaires (filled out by caregiver/study partner)

- *The Amsterdam-IADL (A-IADL) questionnaire short version.* This questionnaire consists of 30 questions that explore the functional capacity during daily living activities as observed in the subjects during the last week. The questionnaire includes several questions regarding the use of media and devices [22]. It is scored by the caregiver/family member, can be operated on tablet or PCs and will take 10 minutes to fill in. (www.alzheimercentrum.nl/professionals/amsterdam-iadl/).

Evaluation of a Computerized Complex Instrumental Activities of Daily Living Marker (NMI) (AltoidaML)

- *Clinical Dementia Rating (CDR)*. The CDR is comprised of a semi structured interview one with the with a caregiver. During the interview, the rater assesses the participant's current status in six domains (memory, orientation, judgment and problem solving, community affairs, home and hobbies, and personal care) and rated accordingly using a 5-point scale (0 = no impairment, 0.5 = questionable impairment, 1 = mild dementia, 2 = moderate dementia, 3 = severe dementia, <http://knightadrc.wustl.edu/cdr/aboutcdr.htm>). The outcome measures of the CDR and CSD-SB are CDR scores (derived from an algorithm developed by the Knight ADRC) [23].
- *Alzheimer's Disease Cooperative Study (ADCS) scale*. ADL in mild and moderate AD subject subscale. A questionnaire describing the performance of activities of daily living in patients with Alzheimer's Disease [24]. ADL in MCI subscale for preclinical and prodromal AD subjects. A questionnaire describing the performance of activities of daily living in patients with mild cognitive impairment [25].
- *Neuro Psychiatric Inventory Questionnaire (NPI-Q)*. A questionnaire to assess 12 neuropsychiatric disturbances, e.g. irritability and depression, in dementia patients [26]. This questionnaire is filled out by a caregiver or informant. All 12 items are scores on severity and frequency.

Performance test at the clinic

- *Navigation and Spatial memory test*:
 - Altoida medical Device test is based on two augmented reality gamified tasks that run on iPAD tablets. In the first task virtual objects (e.g., teddy bears) appearing on the video image captured by the iPAD active camera will be hidden in some specific part of the room and need to be retrieved some minute afterward. A second test require to navigate through the room by watching in the images of the environment transmitted by the camera of the iPAD while a virtual situation of danger and stress (e.g., fire alarm on in the room) is simulated. The execution of these tests requires an active functional engagement of several cognitive dimensions and is captured by the iPAD sensors every seconds. The duration is typically about 15 minutes.
- *Physical functioning tests*:
 - *One minute walking test (1MWT)*. Participants are instructed to walk at a self-chosen comfortable pace for 1 minute through a hallway of 30-50 meters, while wearing validated accelerometers and gyroscopes (Physilog 6, see description below).
 - *One minute dual walking test (1MDT)*. Participants are instructed to walk at a self-chosen comfortable pace for 1 minute through a hallway of 30-50 meters, while wearing validated accelerometers and gyroscopes (Physilog 6, see description below). In addition, participants are instructed to count backwards from 100 in steps of 7 out loud.

Evaluation of a Computerized Complex Instrumental Activities of Daily Living Marker (NMI) (AltoidaML)

- *Instrumented Timed Up and Go (TUG) Test.* Timed Up and Go is a measure of functional lower limb muscle strength that is useful in quantifying functional change of transition movements where subject begins in a seated position, stands up completely, then returns to the sitting position [29]. During this test, subjects will wear a validated accelerometer and gyroscope (Physilog 6, see description below). The duration of the test is about 10 min including the setting of the device.

10. Digital technology Assessments

- *Altoida Medical Device:* Altoida (<https://altoida.com/>) is a mobile phone and tablet-based digital biomarker platform that detects early and subtle micro-errors (accuracy) and micro-movements (latency), which has been shown to be useful in detecting MCI that will progress to dementia years in advance. Using a user-friendly exercise that simulates a complex activity of daily living, the Altoida's Neuro Motor Index (NMI), a score derived from the performance combining data streams from: voice data, hands micromovements and micro-errors, gait micro-errors, posture changes, eye tracking, visuospatial navigation micro-errors etc, provides individually tailored prognostic information with the greatest ecological validity and scalability. Altoida's NMI Medical Device has received DA class II medical device qualification from FDA for the evaluation of perceptual, memory and functional impairment relevant for Activities of Daily living (ADL) and for assisting the diagnosis of MCI & AD in subjects between 55 and 95 years of age. NMI showed a diagnostic accuracy of 94% in predicting cognitive worsening in amyloid positive individuals who converted at MCI due to AD after 5 years [30].

Study teams will be provided with a detailed study operations manual describing the data collection steps for each in-clinic test described above in sections 5.1 and 5.2.

11. Withdrawal of individual subjects

Subjects can withdraw from study participation at any time for any reason if they wish to do so without any consequences. The principle investigator can decide to withdraw a subject from the study for urgent medical reasons.

12. Replacement of individual subjects after withdrawal

Subjects will be replaced in case of withdrawal within 4 weeks after the baseline assessment.

13. Follow-up of subjects withdrawn from treatment

In case of withdrawal, subjects will be asked for their reason for withdrawal. However, they are not obliged to provide a reason for their withdrawal.

Evaluation of a Computerized Complex Instrumental Activities of Daily Living Marker (NMI) (AltoidaML)

14. Premature termination of the study

There are no specific criteria for premature termination of the study.

